8.2 Planned recruitment rate

Accounting for holidays and unforeseeable circumstances (in a COVID-19 era) we originally allowed for 12-months to recruit 730 patients. This equates to 61 patients per month across 18 centres i.e., 3 to 4 patients per month/centre. We believed this is feasible given that the TrEAD study recruited 20 patients per month/centre and estimates from our centres indicate a minimum recruitment rate of 8 patients per month/centre. Recruitment was extended for an additional 12 months following an NIHR monitoring meeting on 17th February 2023 as the original projected targets were not met. During this meeting NIHR agreed for the study sample size to be reduced from 730 to 584. To account for those participants that may not get their reference test performed within the set time frame, a final recruitment target of 600 was agreed with the NIHR in August 2023.

8.3 Internal pilot

A stop-go assessment of recruitment feasibility will be included after a 4-month internal pilot. The 18 sites will be set up in 4 months – 4 in month -1 (before the recruitment period starts, in calendar month 6 of the study), 4 in month 1, 6 in month 2, and the remaining 4 in month 3. Allowing a fallow month for holidays, 4 per centre per month will need to be achieved to reach the target sample size of 730 in 18 sites in 12 months. Recruitment feasibility will be assessed at the end of month 4, when 136 participants should have been recruited. If under 90 or fewer have been recruited, the study may be stopped (Red); between 90 and 114 adapt (more sites and/or more time – AMBER) and if 115 or more continue unchanged (GREEN – within sampling variability of our target). This will be discussed with the TSC and the funder.

During a study monitoring meeting on 17th February 2023 with the funder, NIHR, it was agreed for the study sample size to be reduced from 730 to 584. To account for those participants that may not get their reference test performed within the set time frame, a final recruitment target of 600 was agreed with the NIHR in August 2023.

8.4 Statistical Analysis

The five individual tests (and the sixth exploratory test in four sites) will be compared against the reference test (CTA/MRA), calculating standard diagnostic accuracy metrics of sensitivity, specificity, predictive values, likelihood ratio, and diagnostic odds ratio (using the bivariate model approach implemented in R). 95% confidence intervals calculated at 99% to adjust for the five comparisons will be presented. The robustness of the findings to any observed patterns of missing data will be assessed, which are expected to differ by test. A multiple imputation approach will be used assuming the data are missing at random. In addition, and probably more consistent with the likely missing data generating mechanisms, sensitivity type analyses assuming the data are missing not at random (i.e. informatively missing) will be explored. This would attempt to identify different types of missing data by an underlying reason or reasons, and then imputing values that capture plausible measurements for those missing data. The ?-adjustment approach given by van Buuren will be followed ([Flexible Imputation of Missing Data, Chapman and Hall, 2018, section 3.8ff](#)), and also the recommendations of Molenberghs & Kenward ([Missing Data in Clinical Studies, Wiley, 2007; Section 19ff on sensitivity analyses](#)). These approaches would allow the set of reasons for missing values to vary across the tests. The purpose is to stress the calculated findings to test their robustness to the observed patterns of missing data.

The subgroups of disease severity (both clinically and radiologically defined as detailed below) will be explored and those with/without neuropathy or DFU. The subgroups in the Statistical Analysis Plan will be pre-specified. Any further subgroup analysis (e.g. if suggested later by new data external to the study) will be labelled exploratory. Pre-specified subgroup analyses will be unlikely to be adequately powered. Clinical severity will be graded according to the severity of symptoms (from least to most severe; asymptomatic, intermittent claudication, rest pain and tissue loss). Severity will be measured radiologically using the ANGIO-score as outlined in section 5.7. Both will be analysed as pre-specified subgroup analyses in the Statistical Analysis Plan.

Combinations of tests will be explored to see if using more than one test has incremental diagnostic value. The combinations of tests that were clinically felt to potentially offer an improvement over individual tests will be pre-specified in the SAP, and then, acknowledging the paired data, use the approach of Pepe and Thomson (*Biostatistics*, 2000; 1, 2; 123-140 'Combining diagnostic test results to increase accuracy'), which looks at linear combinations of the underlying tests. Post-hoc checks will be made if there were combinations that were not pre-specified that performed even better, as hypotheses for subsequent evaluation.

It is important to quantify the ability of each of the 5 index tests to measure consistently the same measurement of interest on the same leg of the same subject using the same test kit in the same location and the same environmental conditions, within a short period of time. This quantification of the intra-rater repeatability (or reproducibility) will be undertaken using the test-retest approach (35,36). The inter-rater reliability (the agreement between two or more clinicians measuring the same subject, again as under the conditions above) using appropriate methodology (35,36) will be quantified. For the inter- and intra-rater repeatability, we will aim for a sample size of 100 per pair of index tests.

These reliability studies will be performed at the start of the study and analysed as soon as the data are mature. If an index test has unacceptable intra-rater repeatability, or unacceptable inter-rater reliability, it could be dropped from further consideration, following discussions with the independent TSC. Unacceptable intra- and inter-rater reliability will be assessed in two ways— first, in an absolute sense, by looking at the kappa statistics and using the published guidance as to what an acceptable magnitude is (Fleiss, J.L. (1981). *Statistical methods for rates and proportions* (2nd ed.). New York: John Wiley) with a kappa of <0.4 considered unacceptable. This is not unanimity over interpreting the magnitude of kappa statistics, so our second approach will compare the kappa statistics across the tests, and label unacceptable any tests that are substantially worse than the other tests.

Inter- and intra-rater reliability will also be assessed for the reporting of reference tests using the methods outlined above. Reference tests will not be repeated due to feasibility and ethical considerations.

Full details of the methods and justification of the sample sizes will be included in the comprehensive Statistical Analysis Plan, authored by the study statistician and agreed by the independent TSC. The Statistical Analysis Plan will be prepared and finalised prior to database lock.

Index test diagnostic thresholds

The performance of the index tests based on prespecified diagnostic thresholds for PAD will be evaluated. These thresholds have been selected as they demonstrated optimal

diagnostic performance in the TrEAD study or are commonly used in clinical practice. However, other thresholds have been described in the literature and there is no consensus as to which are best. Therefore, different 'exploratory' thresholds will be evaluated as part of our secondary analyses. Tests generating continuous results (ABPI, TBPI and exercise ABPI) will be evaluated for performance based on optimised thresholds derived from Receiver Operating Characteristics (ROC) analysis. A 'net benefit' approach will be used (as a sensitivity type analysis over a range of plausible thresholds) following ideas for assessing the clinical utility of prognostic models summarised in Riley R et al (*Prognostic Research in Health Care; 2018; Oxford; section 7.4.3 page 168-170*). From this, it should be possible to integrate cost-effectiveness parameters into assessing the best threshold.

Diagnostic thresholds:

- o Visual waveform assessment- monophasic or biphasic waveforms with adverse features.
- o Audible waveform assessment- monophasic waveform
- o ABPI- ≤ 0.9 in either vessel
- o TBPI- < 0.75 in either vessel
- o Exercise ABPI (31)- Post exercise ABPI ≤ 0.9 in either vessel.

Health economics analysis

A literature review will be conducted to identify published health economic studies in similar patient groups. Cost-effectiveness of the tests will be estimated using Markov models that simulate clinical events in a cohort of hypothetical patients with diabetes over 5 years. The structure of the model may follow that developed in previous work by this group (reference 14). Depending on their PAD status (PAD or no PAD), and ulceration status at presentation (DFU or no DFU), patients will be allocated into one of eight initial states following a test: True positive (with and without DFU), true negative (with and without DFU), false positive (with and without DFU), or false negative (with and without DFU).

True and false positive patients without DFU will be prescribed orthotics and additional foot checks, in addition to standard care. True and false positive patients with DFU will undergo confirmatory DUS, and, if confirmed positive, angiography, revascularisation and low dose rivaroxaban, in addition to standard care. True and false negative patients will continue with standard care for the remainder of the 5 year time horizon. The accuracy of test outcomes will be obtained from the study. The probability of clinical events (new DFU incidence and healing rates of DFU, amputation of unhealed limbs, cardiovascular events and death) and treatment effects associated with recommended interventions for diagnosed PAD patients (e.g., orthotics, revascularisation, rivaroxaban) will be obtained from NICE evidence reviews and the literature. The study will be conducted from the perspective of the UK NHS and Personal Social Services according to NICE methodological guidelines and reported according to CHEERS standards. Costs, QALYs, ICERs and measures of uncertainty over 5 years will be estimated. Test costs will be estimated by bottom-up costings during the course of the study that will include machine capital acquisition cost and one-off training (amortised over the useful life and expected through-put of patients per year), consumables and operator time. Prices and unit costs of items will be obtained from manufacturers and national databases.

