5.6 Data collection

A screening log will identify all approached patients and reasons for non-participation.

- Demographics: age, gender, equality and diversity information, diabetes type, history of smoking, retinopathy, chronic kidney disease, ischaemic heart disease, stroke and heart failure
- Foot history: PAD symptoms, previous history of DFU or amputation
- Foot examination: neuropathy, presence of DFU, DFU severity using the WIfI classification system (27)
- Quality of Life questionnaire: the validated EuroQoL (EQ-5D-5L) questionnaire will be used to assess the generic QoL at visit 1.
- Technical success of index tests: inability to perform, refusal and discontinuation of tests will be documented
- Results of index tests
- Evaluation of patient acceptability: patients will be asked to rate their experience of each test on a Likert scale (**Appendix**)

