8. STATISTICAL ANALYSES

8.1 Sample Size and power considerations

Summary of sample size calculations

Assuming PAD prevalence of 50%, with 255 with PAD and 255 without PAD, the study will have 90% power to estimate an assumed sensitivity (or specificity) to a precision of the half width of the 95% confidence interval of 8.2%. For a sensitivity (or specificity) of 80% this half width would increase to 10.2%. The level of significance was set at 1% to adjust for the 5 tests and ensure the overall level of significance does not exceed 5%. Power calculations used R.4.0.0 power.diagnostic.test in package MKmisc. The sample sizes for estimating likelihood ratios will also be estimated.

In the TrEAD study, PAD prevalence was 66%. As there will also be recruitment from primary care, with a lower PAD prevalence (34), the estimate to reflect the findings of our systematic review have been adjusted; prevalence of 50% across 18 studies (11). In TrEAD, TBPI could not be performed in 20% of patients. A similar proportion may be unable to tolerate exercise ABPI. It is estimated that 10% of patients may drop out prior to the reference test. Therefore, the sample size has been inflated by the cumulative missingness across all groups (30%) to be certain of having enough power for each and every test comparison. Thus, we aim to recruit a total of 730 patients.

During a study monitoring meeting in February 2023 with the funder, NIHR, it was agreed for the study sample size to be reduced from 730 to 584 based on the current attrition rate of 13% (as opposed to 30% estimated when the trial was designed). To account for those participants that may not get their reference test performed within the set time frame, a final recruitment target of 600 was agreed with the NIHR in August 2023.

Details of sample size calculations

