3.1 SAP objectives

The objective of this SAP is to describe the statistical analyses contributing to the final report and publication(s) of the DM PAD study. All analyses detailed in the study protocol are addressed with the exception of the internal pilot of the study which will be documented separately.

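### Technical success has no analysis in the SAP, and the economic model does not say how a patient without a test result enters it

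*Protocol*

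**What the plan says.** **Endpoint and data.** Technical success is a listed secondary endpoint (Protocol 2.4). Under Protocol 5.6, "inability to perform, refusal and discontinuation of tests will be documented". Protocol 5.7 also records why exercise ABPI was stopped early or not attempted.

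**Expected failures.** Protocol 8.1 states: "In TrEAD, TBPI could not be performed in 20% of patients. A similar proportion may be unable to tolerate exercise ABPI".

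**Economic model.** In Protocol 8.4, "patients will be allocated into one of eight initial states following a test". The eight are the four accuracy outcomes, each with and without a foot ulcer. On inputs: "The accuracy of test outcomes will be obtained from the study". On structure: "The structure of the model may follow that developed in previous work by this group". Nothing is said about a patient without a result.

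**SAP.** Section 3.1 claims: "All analyses detailed in the study protocol are addressed with the exception of the internal pilot of the study". Section 3.3 makes complete-case analysis the default, tabulates counts of missing values but leaves them out of percentages, and promises a participant flow chart for the primary and secondary analyses. It places health economics outside the SAP, while allowing the statistical results to be used there. Section 3.4 calls a test inconclusive if one vessel is negative and the other is missing; such cases are reported but not analysed. Section 4.6 makes imputation optional. Technical success is not mentioned in the analysis sections.

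**The concern.** A bedside test that cannot be done, is refused, or ends without a usable value gives the clinician no diagnosis. That is an outcome of the test, and it differs between tests: the sponsor's own planning expects it often for TBPI and exercise ABPI.

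The statistical plan treats such a test as missing data and removes it. The economic model then needs a true/false positive/negative split for every patient. If the study's accuracy estimates are fed in as the SAP produces them by default, patients without a result are given the completers' split. A test that often fails is then compared with one that rarely fails as though both always gave an answer.

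At stake is the comparison of tests, both in accuracy and in cost-effectiveness, which is a secondary objective. TBPI was the next best alternative to PAD-scan in the earlier economic model (Protocol, Background), so how its failures are treated bears on a comparison that readers will look for.

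**Working it through.** **1. Was test failure a real design input?** Protocol 8.1 adds 20% test failure to 10% dropout to reach 30%, and needs 510 evaluable participants.

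- 510 / (1 − 0.30) = 728.6, so 729, against the stated 730.
- With the later attrition of 13%: 510 / (1 − 0.13) = 586.2, so 587, against the stated 584.

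Both reproduce closely. Failure was allowed for in the initial sample size, but not in the described model.

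**2. What happens to a failed test under the written rules?** No value is recorded, so SAP 3.3 removes the case. If one vessel is negative and the other missing, SAP 3.4 excludes it. Sensitivity and specificity are then those of completers. Protocol 8.4 takes accuracy from the study and has a place only for the four accuracy outcomes.

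**3. Size.** Let f be the no-result proportion, assumed equal with and without PAD, and Se and Sp the completer values.

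- Failures counted negative: Se × (1 − f) and Sp × (1 − f) + f.
- Failures counted positive: Se × (1 − f) + f and Sp × (1 − f).

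Inputs for TBPI: Se = 60% (TrEAD); Se = 83.0% and Sp = 66.3% (meta-analysis); both are in the Protocol Background. f = 20% is the TrEAD figure in Protocol 8.1. f = 13% is an assumed upper bound: it treats all current attrition as test failure. The other values of f show the range.

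| f | Se 60%, failures negative | Se 60%, failures positive |
|---|---|---|
| 10% | 54.0% | 64.0% |
| 13% | 52.2% | 65.2% |
| 20% | 48.0% | 68.0% |
| 30% | 42.0% | 72.0% |

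At f = 20%, a completer sensitivity of 83.0% becomes 66.4% or 86.4%, and a specificity of 66.3% becomes 73.0% or 53.0%.

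**4. Per 1,000 modelled patients at 50% prevalence and f = 20%.** 200 have no TBPI result.

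- True positives at Se = 60%: 500 × 0.60 = 300 from completer accuracy; 500 × 0.48 = 240 if failures are negative; 500 × 0.68 = 340 if positive.
- False positives at Sp = 66.3%: 500 × 0.337 = 168.5 from completer accuracy; 168.5 × 0.80 = 134.8 if failures are negative; 134.8 + 100 = 234.8 if positive.

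**5. Effect on a comparison.** TrEAD gives TBPI and ABPI the same sensitivity, 60%. If ABPI never failed (an assumption; the documents give no rate), the tie at 60% would become 48% or 68% for TBPI against 60% for ABPI.

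**The case against.** Several objections have force.

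- **The SAP does deal with absent results.** A reader might infer that it ignores them. It does not: it tabulates missing counts, draws a flow chart, reports inconclusive tests and allows imputation, and Protocol 8.4 plans analyses under data missing at random and not at random, by reason. This stands as a limit on the point. But none of these gives a failure proportion per test by reason, and imputation assigns a result to a test that gave none.
- **Economics is outside the SAP, and the model structure is provisional.** Both are true. The gap in the model belongs to Protocol 8.4 or a separate economic plan, and the use of completer accuracy is what the default implies, not something that the protocol states.
- **The existing eight states can hold failures.** A reader might infer that the model needs new states. It does not; what is missing is the rule that allocates patients without a result.
- **The 20% is weak.** It is one earlier study's TBPI figure, and a guess for exercise ABPI. Attrition was later put at 13%, not split by cause. The 20% can serve only as an illustration.
- **A stopped test may still give a value.** Protocol 5.7 lets exercise end early and still describes measuring ABPI afterwards. Discontinued and without result are not the same.
- **SAP 3.1 may be literally right.** It speaks of analyses detailed in the protocol, and Protocol 8.4 details none for technical success. A reader might call the SAP statement false; the firmer point is that a listed endpoint has no analysis.

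A reader might also infer that the plan favours TBPI and exercise ABPI in QALYs, costs and ICERs. The documents do not support this. If failures count as negative, detected cases fall but so do false positives and the care that follows them; if they count as positive, sensitivity rises above the completer value. No ICER can be computed from what is given.

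**Conclusion.** The point holds in limited form. A listed secondary endpoint with data collected has no analysis. Followed as written, the SAP defaults and Protocol 8.4 together would apply completer accuracy to patients whose test gave no result. This can bias comparisons between tests with different failure rates, but its direction is not fixed.

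For TBPI at 60% sensitivity, the gap between the two ways of counting failures is 20 percentage points at 20% failure (48% to 68%) and 13 points at 13% failure (about 52% to 65%). These figures assume equal failure with and without PAD. The 13% bounds test failure only if current attrition covers the same losses as the 30% it replaced. Equal failure may not hold by ulcer status: Protocol 5.7 links inability to do exercise ABPI to foot deformity, amputation and ulceration, and ulcer status is a stratum of the model.

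**What to change.** **In the SAP**

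1. Report technical success for each index test: n/N with all recruited participants as denominator, 95% CI, by reason (not possible, refused, stopped without a value, inconclusive), and by PAD status among those with a reference result. Count a stopped test that still gave a value separately.
2. Add a secondary accuracy analysis that keeps failed, refused and inconclusive tests in the denominator, counted once as negative and once as positive, beside the complete-case estimates.

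**In Protocol 8.4 or the economic plan**

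3. Feed each test's observed no-result proportion, by ulcer and PAD status, into the model. State how these patients are allocated, which can use the existing eight states, and vary the allocation in scenario analyses. The clinical pathway after a failed test is for the investigators to define.

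**Cost.** A short SAP addition, a few extra tables and some extra model runs, from data that Protocol 5.6 already collects. Tests that often fail may be shown with less favourable performance.

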9. REGULATORY, ETHICAL AND LEGAL ISSUES

9.1 Declaration of Helsinki

The investigator will ensure that this study is conducted in full conformity with the 2013 revision of the 1964 Declaration of Helsinki.

9.2 Good Clinical Practice

The study will be conducted in accordance with the guidelines laid down by the International Conference on Harmonisation for Good Clinical Practice (ICH GCP E6 guidelines).

9.3 Research Ethics Committee (REC) Approval

(i) Initial Approval

Prior to the enrolment of participants, the REC must provide written approval of the conduct of the study at named sites, the protocol and any amendments, the Participant Information Sheet and Consent Form, any other written information that will be provided to the participants, any advertisements that will be used and details of any participant compensation.

(ii) Approval of Amendments

Proposed amendments to the protocol and aforementioned documents must be submitted to the REC for approval as instructed by the Sponsor. Amendments requiring REC approval may be implemented only after a copy of the REC's approval letter has been obtained.

Amendments that are intended to eliminate an apparent immediate hazard to participants may be implemented prior to receiving Sponsor or REC approval. However, in this case, approval must be obtained as soon as possible after implementation.

(iii) Annual Progress Reports and End of Trial Notification

The REC will be sent annual progress reports in accordance with national requirements and will also be informed about the end of the trial, within the required timelines.

